These studies will provide a clinical basis on the weight reducing effect of high protein diet and the associated alterations in the profile of postprandial gut hormones released, and unravel the underlying mechanisms at the neuronal (vagal afferent) level in an experimental model of obesity. The proposed studies will address important pathophysiological questions regarding the mechanisms regulating satiety/body weight as well as provide potentially important clinical treatment strategies.

NARRATIVE

[figure not shown]
Obesity is rapidly becoming an epidemic within the VA Healthcare System. It is associated with the development of metabolic syndrome in addition to type 2 diabetes and hypertension. Accordingly, the overarching goals of this proposal are to identify the mechanisms responsible for the development of obesity and to identify potential therapeutic targets that can be used to treat this condition. The utility of a high protein dietary intervention to modulate the vagal nervous system and modulate the gastrointestinal microbiome are being proposed herein. In preliminary studies, we have demonstrated in both rodents and in humans that a high protein diet effectively and safely results in a reduction in body weight and alteration of the gut microbiome to favor an anti-obesity phenotype. Given that the VA Medical Care System is the largest of its type in the USA, and that the 158 medical facilities include over 5 million patients, strategies to reduce the incidence of obesity-related morbidity and mortality are likely to have a beneficial impact not only on patient care through prevention but will result in a significant savings in resources that could be better spent on other aspects of veteran healthcare.

RESEARCH PLAN

1. RATIONALE

A. Statement of the Problem.

Obesity has become endemic in the United States. It is estimated that about one third of our population is obese.^(1,2) The health consequence of obesity involves increased risk of developing adult onset type II diabetes mellitus, dyslipidemia, arteriosclerosis and certain forms of cancer, including colorectal and

pancreatic cancer.⁽¹⁾ Therefore, obesity represents a major medical problem in the United States and 6% of entire health care costs are spent taking care of obesity-related co-morbidities. A modest 5 to 10% of body weight loss in obese subjects has been shown to result in improvements of these metabolic disturbances.⁽³⁾ Successful treatment of obesity not only requires an approach that involves a combination of dietary, behavioral modifications and exercise⁽¹⁾ but also requires a greater understanding of the regulation of appetite and satiety. These approaches will lead to innovative therapies to improve treatment. The use of a high protein diet has become a popular method to achieve a reduction in body weight,⁽⁴⁾ however the means by which an isocaloric high protein diet influences satiety is not understood.

Evidence indicates that the gastrointestinal (GI) tract acts as nutrient sensor resulting the release of gut hormones or transmitters that play an important role in the control of satiety, feeding behavior and, hence, body weight.⁽⁵⁻⁹⁾ Neuropeptides and GI hormones regulate the neural pathways interconnecting peripheral stimuli to the brain.⁽⁹⁾ Our team, based at the VA Greater Los Angeles Healthcare System, has a long history in the study of GI hormones and their physiological and cellular mechanisms. In addition, we were among the first to provide evidence that GI peptides activate specific brain nuclei involved in the regulation of feeding behavior and the autonomic nervous system⁽¹⁰⁻¹²⁾. Although the focus of our group has been mainly the endocrine, neuronal and chemical regulation of gastric secretion and motility, we are now expanding our focus to obesity, which plays an important role in the health of our veteran patients. Therefore, using our knowledge of GI hormones and gut-brain interactions, the overall objective of this proposal is to further establish that a high protein diet reduces body weight in obese patients and to unravel the physiological basis for the effects of this diet. Specifically, we will test the effect of high protein diet on changes in weight, the microbiome, and neuropeptides released in obese patients and elucidate the underlying physiological mechanisms in animal models.

B. Hypotheses/Kev Questions.

GI signals contributing to energy balance are abnormal in patients with obesity disorders. Levels of hormonal peptides are likely regulated by high protein diets that have been shown to result in weight loss.^(5,9) These GI hormones may be regulated by signals from the intestinal microbiome, which we have shown in unpublished data is altered by a high protein diet. We therefore hypothesize that a high protein diet shifts the microbiome to induce a differential pattern of GI hormone release leading to early satiety signaling.

The objectives of this proposal, accordingly, are to corroborate data from our preliminary human studies showing that a high protein diet results in body weight loss. We will correlate the observed clinical findings with an understanding of normal and pathological appetite regulatory mechanisms in experimental animals. In order to accomplish the stated goals of this program, we have brought together interdisciplinary collaborations at our VA Medical Center from diverse backgrounds including: microbiome, cell biology, molecular biology, neurophysiology and human clinical investigations, including health services research to investigate the mechanisms regulating feeding behavior and obesity. Our proposal is focused on addressing three hypotheses linking clinical and translational approaches that are critical to understanding the pathophysiology of satiety/obesity.

1. A higher protein replacement diet will result in early satiety signaling and weight loss in obese patients and a differential pattern of postprandial GI hormone release.
2. Patients on the high protein diet will have shifts in the composition and function of their intestinal microbiome.
3. Abundance of specific fecal microbes can be used to predict response to a high protein diet.

C. Specific Objectives.

AIM 1: To Confirm the Hypothesis that a High Protein Diet Reduces Body Weight and Alters the Pattern of Postprandial Gut Hormone Release in Obese Patients.

Rationale: In the first aim, we will evaluate whether an isocaloric high protein diets (1 gram of protein per pound of lean body mass) will improve weight loss in comparison to a standard protein diet based on 0.5 gram of protein per pound of lean body mass. Our preliminary studies support the concept that a higher protein meal replacement will result in significant losses of body mass in obese subjects and that a high endogenous level of ghrelin in patients with neuroendocrine tumors results in increased weight gain. In the study, bioelectrical impedance will be used to determine the protein requirement at the level of 0.5 or 1 gram per pound of lean body mass. Weight loss will be the primary outcome. A secondary variable will include satiation as measured using a standard questionnaire, liver stiffness as determined by transient elastography, and microbiome changes determined by 16S sequencing. In addition, we will establish the changes in the levels of the orexigenic peptide ghrelin including the ratio of ghrelin to des-acyl ghrelin, and anorexigenic peptides PYY, leptin, CCK, GLP-1 and nesfatin-1 following high protein meal ingestion.

AIM 2. Characterize the changes in the fecal microbiome induced by a high protein diet

Rationale: Diet induces rapid changes in microbial composition and is associated with long-term microbial community structure^(13,14,30-32). Recent advances in the microbiome field suggest that intestinal bacteria may be involved in the response to a HPD. Germ-free mice have lower body fat and resistance to diet-induced obesity that are rapidly reversed upon microbial colonization, attributed to increased nutrients from microbial digestion of complex plant polysaccharides and elevated levels of a lipoprotein lipase inhibitor (Fiaf)^(15,16). It was subsequently shown that obese humans and mice have distinct intestinal microbiome composition from controls, characterized at the phylum level by an increased ratio of Firmicutes to Bacteroidetes⁽¹⁷⁻¹⁹⁾. This ratio decreased in subjects who lost weight on either a carbohydrate-restricted or fat restricted diet⁽²⁰⁾. There is now considerable evidence that the composition of the intestinal microbiome influences susceptibility to obesity. Colonization of germ-free mice with the microbiota of obese mice (induced by leptin-deficiency or a Western diet) results in increased body fat accumulation compared to colonization with microbiota from lean controls^(18,19). Similarly, germ-free mice colonized with feces from obese humans had increased adiposity on a high fat diet than germ-free mice colonized with feces from lean humans in weight discordant twin pairs⁽²¹⁾. Moreover, susceptibility of mice deficient in Toll-like receptor 5 and inflammasome components to diet-induced obesity was transmissible to other mice by fecal transplantation^(22,23). Intestinal microbiota that predispose to obesity are believed to increase extraction of calories from ingested food. Supporting this, obese mice have higher levels of bacterial genes involved in complex polysaccharide digestion, decreased residual energy in feces, and increased short chain fatty acids⁽¹⁸⁾. The obese human microbiome has elevated levels of genes in phosphotransferase pathways involved in bacterial carbohydrate metabolism⁽²⁴⁾.

Recent data suggests that the intestinal microbiome can mediate the response to anti-obesity interventions. Roux-en-Y gastric bypass and vertical banded gastroplasty are associated with long-term alterations of the intestinal microbiome in humans and mice⁽²⁵⁻²⁷⁾. Colonization of germ-free mice with post-bariatric surgery feces resulted in less fat accumulation on standard mouse chow compared to colonization with stool from non-surgical obese patients⁽²⁶⁾. Animal models have highlighted the contribution of *Akkermansia*, a genus that is depleted in obese mice and humans but enriched after gastric bypass surgery^(25,27,28). Colonization of germ-free mice with the microbiome of mice following gastric bypass surgery resulted in weight loss and reduced adiposity compared to recipients of sham operated mice, associated with increased *Akkermansia*⁽²⁷⁾. Daily gavage of live but not heat-killed *Akkermansia muciniphila* reduced adiposity and hyperglycemia in mice with diet induced obesity⁽²⁸⁾. Interestingly, metformin treatment of mice on a high fat diet increases *Akkermansia muciniphila*, which has been proposed as a mechanism of its therapeutic effect⁽²⁹⁾. We recently demonstrated in a rodent model of Western diet-induced obesity that a high protein diet induces *Akkermansia muciniphila*, just as had been seen after bariatric surgery. Abundance of *Akkermansia muciniphila* was inversely correlated with body fat mass. Based on our preclinical rodent model data, we hypothesize that a high protein diet will shift the composition of the microbiome of obese subjects, including increased *Akkermansia*, and that this will result in an altered metagenome (abundances of bacterial genes).

AIM 3. Identify fecal microbial predictors of response to a high protein diet.

Rationale: We hypothesize that subjects will vary in the responsiveness of their microbiota to a HPD based on baseline or post-dietary intervention levels of microbes such as *Akkermansia muciniphila* that respond to the HPD. We will determine the time course of shifts in the microbiome and correlate these changes to weight loss and other metabolic parameters. Further understanding of the link between the microbiome and the beneficial effects of a high protein diet may spur development of therapies for obesity that directly target the microbiome to complement dietary modification.

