two groups. The data for all time points will then be fitted to a multivariate model under a negative binomial distribution using DESeq2 with diet group, time point, interaction between diet and time point, baseline BMI, age, sex, and smoking status as covariates. This model will be compared to a reduced model that does not include the diet:time point interaction⁽⁷⁰⁾. A likelihood ratio test will be used to identify microbes with differential abundance by diet at time points after baseline. Estimates of significance will be adjusted for multiple hypothesis testing⁽⁷¹⁾. OTUs that are differentially abundant on a HPD will be grouped by hierarchical clustering, which we anticipate will highlight distinct kinetic patterns of microbial change.

Expected results/potential pitfalls: We do not anticipate problems with the collection or transportation of fecal samples to our clinical research unit. We predict that *Akkermansia* will significantly increase on a HPD as was seen in our rodent studies. We further predict that most HPD-responsive microbes will have altered abundance within the first 3 to 7 days as has been observed in other dietary studies^(72,73). We estimate a 20% dropout rate based on our high protein meal replacement study, leaving approximately 80 subjects per group. This compares favorably to published studies reporting dietary effects on the microbiome using sample sizes of 10-15^(72,73,74). We anticipate that a HPD will have a similar magnitude of effect as these previously studied diets and hence we expect to have sufficient numbers to detect compositional differences.

2.2 Identification of metagenes affected by a high protein diet.

Experimental protocol: We will assess the functional consequences of altered microbial composition by sequencing the genes carried by intestinal microbes. Shotgun sequencing of DNA extracted from fecal samples will be performed using the HiSeq 3000 with a target depth of 10 GB data per sample, comparable to the 11.7 GB depth used by the Human Microbiome Project for stool samples⁽⁷⁵⁾. Due to the costs of sequencing at this depth, we will only sequence baseline samples and samples from day 112.

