Study design: This is a randomized study using the same subjects described in Aim 1. Nutritional assessment, physical examination, bioelectrical impedance, laboratories will be performed at baseline, and weeks 2, 4, 6, 8, 12 and 16. Stool samples will be collected on day 3, 7, 14, 17, 21, 28, 42, 56, 84 and 112.

Study timeline: Data collection will be completed at week 16. The stool samples collected during the study period will be used for 16S rRNA sequencing, shotgun metagenomics, and data analysis.

Bioinformatics protocol: Patient characteristics (physical measurements, lean body mass, laboratories, demographic traits) at baseline will be compared using a 2-sided t-test (for numerical variables) or chi-square test (for categorical variables) to evaluate the randomization. 3DFR and FFQ performed at each timepoint will be used to assess the predicted protein content of the patient's diet compared to baseline to evaluate the success of the dietary intervention. Clinical response endpoints significantly associated with HPD in Aim 1 will then be correlated with the abundance of microbes found to be enriched or depleted on a HPD in Aim 2.1. These endpoints will be fitted to multivariate models to adjust for baseline clinical covariates including BMI, age, sex, and smoking status. Spearman correlations will then be calculated for all combinations of residuals for the clinical endpoints and for microbial abundance (using DESeq2 fitted multivariate models from Aim 2.1 to adjust for covariates). Separate correlation analyses will be performed at baseline and each of the time points during treatment.

Microbes that are independently associated with clinical response to a HPD will then be used to create random forests classifiers to predict response. Subjects in the HPD group will be identified as responders if they had a decrease in any of the clinical endpoints that exceeded the predictions of the multivariate model for the NPD group. The sensitivity and specificity of the classifiers will be estimated using 10-fold cross-validation. Classifiers constructed from baseline microbial abundance and microbial data at each time point will be compared to determine the earliest time point when accurate predictions of response are possible.

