The above analytic pipeline will then be applied to the shotgun metagenomics data obtained at baseline and day 112. Gene families and/or metabolic pathways that shift in response to a HPD may be more consistent across diverse populations than abundance of specific microbes such as *Akkermansia* which could vary greatly from person to person⁽⁷⁸⁾. The performance of classifiers constructed from metagenes will be compared to those built from microbial abundance to identify the approach that is most predictive for response.

Expected results/potential pitfalls: We predict that a subset of the HPD-associated microbes and metagenes will be associated with response in the HPD. We also expect that baseline and/or post-dietary intervention abundances of microbial features can be used to generate accurate random forests predictors for clinical response. We used similar bioinformatics approaches to identify the inverse correlation of *Akkermansia muciniphila* with body fat in our rodent model and to predict IBD status in families with pediatric inflammatory bowel disease. Accordingly, we do not anticipate problems performing these analyses.

Human Subjects

1. Risk to Subjects

(a) Human Subjects Involvement and Characteristics:

Approximately 198 healthy volunteers age 30 years and older between BMI of 27 to 40 kg/m² will be able to take part in this study. Pregnant women or women likely to become pregnant during the course of the study may not participate in this study. Female subjects must not be

able to conceive by reason of surgery, radiation, 1 year past the onset of menopause, or an approved method of contraception. No vulnerable subjects will be included in the study. (See the detail in the Research Plan, Proposed Work, Aim 1, Sections of Recruitment, Procedures, and Statistical Analysis)

(b) **Sources of Materials:** See the detail in the Research Plan, Proposed Work, Aim 1, Section of Procedures.

(c) **Potential Risks:**

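### Aim 3 promises to relate changes in the microbiome to weight loss, but the only planned correlation uses covariate-adjusted abundance at each visit, with nothing to separate a subject's shift from the starting level

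*Combined protocol and SAP*

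**What the plan says.** Section 1.C, Aim 3 rationale, states the question in terms of change: "We will determine the time course of shifts in the microbiome and correlate these changes to weight loss and other metabolic parameters". The sentence before it frames the hypothesis differently, in terms of levels. With *Akkermansia muciniphila* as its example, it expects responsiveness to differ "based on baseline or post-dietary intervention levels of microbes such as" this one.

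Section 4.C, Bioinformatics protocol, gives the analysis. Aim 1 endpoints that respond to the high protein diet (HPD) "will then be correlated with the abundance of microbes found to be enriched or depleted on a HPD in Aim 2.1". On the scale used, it says: "Spearman correlations will then be calculated for all combinations of residuals for the clinical endpoints and for microbial abundance". The adjustment on the microbial side is described separately, as "using DESeq2 fitted multivariate models from Aim 2.1 to adjust for covariates". On timing: "Separate correlation analyses will be performed at baseline and each of the time points during treatment". The random forest classifiers also use abundance at baseline or at a given visit. The same pipeline is then applied to the shotgun data from baseline and day 112.

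Section 4.B, Aim 2.1, defines the model behind the microbial residuals. Besides main effects of diet and visit, it has the "interaction between diet and time point, baseline BMI, age, sex, and smoking status as covariates". Section 4.C adds that the abundance of specific microbes such as *Akkermansia* is something "which could vary greatly from person to person".

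**The concern.** The stated question is whether subjects whose microbiome moves more on the diet lose more weight. The planned variable is where a subject's microbiome stands at a visit. These differ whenever people start from different places and tend to stay there, and the protocol itself expects large differences between people.

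Two things are at stake. If weight loss follows the shift, stable variation between people acts as noise in the visit-level abundance and can weaken the association. If weight loss follows only the level a subject brought into the study, that level is still present at every later visit. It can then give significant on-treatment correlations that read like an effect of the dietary shift.

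**Working it through.** **What the residual contains.** Write a subject's log abundance at visit t as (group-by-time mean) + (effects of BMI, age, sex, smoking) + a + d(t) + e(t). Here a is the subject's own remaining stable level, d(t) is that subject's departure since baseline, and e(t) is sampling noise. The Aim 2.1 covariates remove the first two terms. The on-treatment residual is a + d(t) + e(t), and the baseline residual is a + e(0). No change score, baseline-abundance covariate or subject effect removes a. The Aim 2.1 likelihood ratio test does examine shifts, but between groups. It does not link one person's shift to that person's weight loss.

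**Sample size.** Study Design gives 100 per arm and 20% dropout: 100 × (1 − 0.20) = 80, which matches the roughly 80 per group stated under Aim 2.1. Aim 3 has no power statement of its own.

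**Simple model.** The documents give no variances or correlations, so these are assumptions. Baseline B and shift D are independent with unit variance, and the visit level is P = ρB + √(1 − ρ²)·D. The outcome correlates r = 0.35 with either D or B. The correlation that the plan would estimate is then:

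- outcome follows the shift only: r√(1 − ρ²)
- outcome follows the baseline level only: rρ

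| ρ | shift only | baseline only |
|---|---|---|
| 0.3 | 0.35 × 0.954 = 0.334 | 0.105 |
| 0.5 | 0.35 × 0.866 = 0.303 | 0.175 |
| 0.7 | 0.35 × 0.714 = 0.250 | 0.245 |
| 0.9 | 0.35 × 0.436 = 0.153 | 0.315 |

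Noise of variance v in each sample divides these by √(1 + v).

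Hand check at ρ = 0.7 without noise: atanh(0.250) × √77 = 0.255 × 8.775 = 2.24, and 2.24 − 1.96 = 0.28, which gives power of about 61% for a Pearson test. The simulated Spearman test gives 57%.

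**Simulated two-sided Spearman tests at 0.05, n = 80** (repeat runs of a cell differ by a few points):

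- No noise, shift only: levels 57% (ρ = 0.7) and 25% (ρ = 0.9); baseline-adjusted 86% at both.
- No noise, baseline only: levels 55% and 77%; baseline-adjusted 5% at both.
- Noise variance 0.25, shift only: levels 48% and 21%; adjusted 64% and 36%. False signal after adjustment when only baseline matters: 8% and 11%.
- Noise variance 0.49, shift only: levels 40% and 21%; adjusted 49% and 28%. False signal after adjustment: 10% and 15%.

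Over ρ from 0.3 to 0.9 and noise variance from 0 to 0.49, power is about 17-81% with levels and 26-86% with adjustment. When only baseline matters, about 11-77% of visit-level tests are significant, against about 5-16% after adjustment.

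**Second model.** This one has separate variances for stable level, shift and noise, with covariates explaining 20% of the stable level (n = 80, 2,000 runs per scenario). The outcome correlates 0.5 with the shift only, or 0.4 with the stable level only. Entries are level / change score / baseline-adjusted level.

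| stable : shift : noise | power, shift only | significant, stable level only |
|---|---|---|
| 4 : 1 : 0.5 | 51 / 86 / 87% | 79 / 5 / 9% |
| 2 : 1 : 0.5 | 69 / 88 / 89% | 70 / 6 / 12% |
| 1 : 1 : 1 | 73 / 70 / 78% | 45 / 5 / 20% |
| 0.5 : 1 : 1 | 79 / 69 / 80% | 27 / 6 / 17% |

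Baseline adjustment has the highest power in every row, though in the last row its lead over levels is one point. A plain change score does worse than levels in the two noisier rows.

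**The case against.** Several stronger readings are tempting, and the documents do not support them.

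- *The plan correlates raw abundance.* It does not. Section 4.C specifies covariate-adjusted residuals. The gap is that the subject's own starting level is not among the things adjusted for.
- *Levels are the wrong variable for Aim 3.* The hypothesis also concerns baseline or on-diet levels, and the classifiers look for the earliest visit at which response can be predicted. Levels suit both. The gap is one stated question without a matching analysis.
- *A pre-existing difference would go unnoticed.* The plan runs the same correlation at baseline. When only the starting level matters, that correlation is significant in about 85% of runs in the simple model without noise, and in 43-89% in the second model. It would often expose the problem. However, the plan gives no rule for comparing baseline and on-treatment results, and if both are significant the reader still cannot tell whether the shift adds anything. It also recovers no lost power.
- *Microbes are screened first.* Only those with a diet effect in Aim 2.1 go forward. That screen works on group means and leaves individual starting levels in place.
- *The planned analysis cannot detect a shift association, or hides it.* Levels attenuate the association without removing it. At a within-person correlation of 0.5 without noise, power with levels is still about 75%.

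The sample size is also open. The protocol restricts the responder definition to the HPD group but does not say whether the correlations use one arm or both. With about 160 subjects, level power at ρ = 0.7 without noise rises to 86%, but the share significant from baseline alone rises to 84%.

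**Conclusion.** The mismatch holds on the text: a correlation of changes is promised, and only correlations of adjusted levels are specified. An on-treatment correlation from this plan cannot by itself be read as evidence that the dietary shift tracks weight loss.

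The size is uncertain, because the within-person correlation, the noise and the true correlation are all assumed. The loss is large when people differ stably and samples are precise, and small when the within-person correlation is low. The 86% power and 5% false-signal figures for baseline adjustment are a noise-free best case. With noise, power under adjustment falls to 26-77% and some false signal remains (6-16% in the simple model, 9-20% in the second).

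This is an exploratory step in the third aim. It does not touch the primary endpoint, safety or the trial's sample size. Severity is low to moderate.

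**What to change.** Keep the planned level correlations for the level hypothesis and the classifiers. For each post-baseline stool time point, and for the day-112 metagenes, add a correlation of the clinical endpoint with abundance adjusted for the subject's own baseline abundance, for example a partial Spearman correlation given baseline abundance. State that any claim about diet-induced shifts rests on this added analysis, that the baseline correlation tests pre-existing predictors, and which arm or arms each correlation uses.

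The analysis needs a baseline stool sample. The stool-day lists (Fecal Sampling under Aim 1, and Study design under Aims 2 and 3) start at day 3, whereas Study Visits includes stool among the week 0 assessments and Aim 2.2 relies on baseline samples. These should be reconciled.

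The cost is SAP wording and slightly more analysis work. Subjects without a baseline sample drop out of the added correlations, and sampling noise leaves some residual leakage from the starting level, which the report should acknowledge.
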